Mechanism: IPT enables participants to participate in discussions through which they learn and implement strategies to reduce conflict and build relationships.

Outcome: This generates reductions in depression.

CMOC 3

Context: For boys who do not experience cultural norms or structural violence which impede opportunities to implement new strategies.

Mechanism: IPT enables participants to participate in discussions through which they learn strategies to develop hope, reduce conflict, build relationships and improve self-efficacy.

Outcome: This generates reductions in depression.

CMOC 4

Context: For older (and more cognitively able?) students more cognitively able to consider others' perspectives, learn negotiation skills, develop solutions to interpersonal problems, understand links between events and mood, manage anger and name and express emotions.

Mechanism: IPT enables participants to participate in discussions through which they learn strategies to develop hope, reduce conflict, build relationships and improve self-efficacy. Measure cognitive ability to understand and apply skills (knowledge quiz) – could also consider a self assessment of skills

Outcome: This generates reductions in depression.

CMOC 5

Context: For students participating in initial sessions and participating in discussions which validate participants' experiences and instil hope.

Mechanism: IPT enables participants to develop hope and motivation to engage in the intervention.

Outcome: This generates immediate reductions in depression.

We will refine the CMOCs by analysing qualitative and quantitative process evaluation data. Table 5 lists these data. In addition to data collected through the trial and process evaluation we will also conduct semi-structured interviews with 30 adolescents (20

depressed and 10 non-depressed) from schools which are not participating in the trial. In these interviews we will specifically explore themes from the CMOCs including age, gender, socioeconomic status and school climate and how they influence adolescents' experiences of depression.

Cost analysis

We will do an activity-based cost analysis of the implementation of IPT from the provider perspective. Costs from monthly project accounts will be entered in an Excel tool, divided into start-up or implementation costs, and allocated to different cost centres (capital, staff, and materials) and intervention activities (e.g. adaptation, training, facilitation, etc.). Through interviews with project staff members, we will collect information about how they divided their time across activities and thus how to allocate their salaries. The total cost of the intervention will be annualised then divided by the number of participants in a year to estimate a unit cost per IPT participant.

Incentives

We will cover transportation costs incurred by adolescents and adults participating in the process evaluation and they will also be offered refreshments (juice and biscuits). Phone credit will be offered as an incentive to adolescents and caregivers participating in the surveys.

Post-trial care

Where required, a psychosocial counsellor employed by TPO Nepal will remain in the study setting to provide follow-up care for participants.

Ethics

We have ethical approval from the Nepal Health Research Council (ref no. 701) and King's College London Research Ethics Committee (HR/DP-22/23-37705).

At the school level, we will take written consent from the school principal to screen adolescents and for randomisation. Eligible adolescents who wish to participate in the trial will be asked to take home a written information sheet and consent form. We will obtain written consent from adolescents which will be collected before the baseline survey is conducted. For adolescents aged 17 and younger we will take consent from their caregiver

and adolescent assent. We will obtain written consent from any caregiver, teacher or IPT facilitator from whom we collect data.

Disclosures of suicidality will be handled according to the type of participant.

i) Trial participants

All potential adolescent trial participants will be assessed for suicidality at screening and those identified as high risk (i.e., current suicide plan or attempt in the last three months) will be excluded from the trial and referred to the psychosocial counsellor for further assessment and safety planning, referrals and follow-up. Adolescents participating in the trial will be assessed for suicidality in each survey. Facilitators will assess intervention participants for suicidality in pregroup and group sessions. If a participant is identified as high risk (i.e., current suicide plan or attempt since last assessment), the research assistant or facilitator will activate a standard operating procedure (SOP) which involves alerting the project coordinator and linking with the clinical team. Participants who are not high risk but disclose suicidal ideation at any given time will be given the number of the suicide hotline where they can receive support 24/7. All participants will be provided with a contact number for the project team to call in the event of an emergency.

i) Process evaluation participants

- a. If an adolescent discloses suicidality to a research assistant we will follow the SOP for suicide to assess risk and inform management and referral.
- b. Adults Caregivers who disclose suicidality will be given information about trained local health workers. The SOP for suicide can be triggered anytime a research assistant has a reason to suspect suicidal risk, as indicated in the SOP, or whenever a participant approaches a research assistant, or any research team member expressing safety concerns. The same procedure will be followed if risk is identified among caregivers, facilitators, teachers, nurses, or school principals.

There is a separate SOP for disclosures of abuse which includes a safety assessment and planning and potential referral to the women and children government officer attached to the local municipality, or to the local primary health care centre where physical and mental health problems can be further assessed and managed.

Harms

There are no anticipated harms for participants or schools but there may be unanticipated harms. We will assess these by analysing outcomes at endline and follow-up, by collecting information on any adverse events, and exploring potential harms through the qualitative interviews and FGDs in the process evaluation. King's College London is the sponsor. There will not be a Data Safety and Monitoring Board (DSMB) for the pilot trial. Any serious adverse events will be reported immediately to the Trial Steering Committee (TSC) who will decide what action should be taken. We will report other adverse events to the TSC at follow-up.

Trial registration and conduct

We have registered the trial with the ISRCTN registry. We will follow MRC Guidelines for Global Health Trial Management.

Dissemination

We will publish findings from the pilot trial including the process evaluation and analysis of realist data in academic journals. We will organise dissemination events in Chitwan and Kathmandu, with national and local government officials, adolescents, caregivers, teachers, researchers and non-governmental organisations.

Timeline

Figure 7 presents the SPIRIT enrolment, intervention and assessment schedule.

Trial status

As of July 2024, recruitment is complete. IPT groups have finished in all three strata. Endline and follow-up surveys are ongoing.

Tables

Table 1: Research questions and data sources

Question	Data sources
Is it feasible to deliver IPT in	Proportion of planned IPT sessions delivered
secondary schools in Chitwan?	Focus group discussion and interview transcripts with IPT facilitators, adolescents, teachers
	and caregivers
Is the intervention acceptable to	Proportion of adolescents who consent to participate in the trial
participants?	Proportion of IPT sessions attended by intervention participants
	Proportion of all schools invited who agree to participate in the trial
	Intervention participant treatment satisfaction surveys
	Focus group discussion and interview transcripts with intervention participants
Is the intervention acceptable to	Focus group discussion and interview transcripts with caregivers and teachers
caregivers and teachers?	
Is it feasible to train and supervise	Therapeutic competency assessed with ENACT and GroupACT tools
local lay people to deliver IPT?	Intervention fidelity assessed with the IPT checklist
	Proportion of facilitators trained who pass a paper-based IPT knowledge test
	Proportion of IPT sessions observed by supervisors
	Number and type of adverse event and response
	Focus group discussion and interview transcripts with intervention participants and facilitators
Are trial procedures	Proportion of eligible adolescents and schools that consent to participate in the trial
(randomisation, masking, data	Baseline, midline, endline and follow-up survey response rates
collection, safety standard	Proportion of schools that consent to participate and are retained throughout the trial

operating procedures, control	Focus group discussion and interview transcripts with IPT facilitators, adolescents, teachers
conditions) feasible to implement	and caregivers
and acceptable to participants and	Caregiver survey response rates
schools?	Rates of missing items on trial outcomes
How reliable are the measures for	Research assistant inter-rater reliability for primary and secondary outcomes
trial outcomes?	Internal consistency of each outcome measure
What are the recruitment, retention	Proportion of eligible adolescents and schools that consent to participate in the trial
and response rates for trial	Proportion of trial participants and schools retained at endline
participants?	Trial participant baseline, midline, endline and follow-up survey response rates
How does context affect	Focus group discussion and interview transcripts with IPT facilitators
implementation of IPT?	Recruitment, retention and response rates by gender, school, age
Do data from the process	See Table 5
evaluation support or refute	
CMOCs?	
What are the costs per participant	Cost data
of implementing IPT in schools in	Time sheets
Chitwan?	Interviews with SAATHI-2 team members

Table 2: Progression criteria

Research question	Criterion	Indicator	Green	Amber	Red
Is it feasible to deliver IPT in	Intervention	Percentage of planned IPT sessions	>70%	40-70	<40
secondary schools in Chitwan?	implementation	delivered			
Is the intervention acceptable	Participant treatment	Percentage of participants rating IPT as	>67	30-66	<30
to participants?	satisfaction	'quite helpful' or 'very helpful';			
	Treatment adherence	Percentage of participants who attend	>50	20-50	<20
		more than 70% of IPT group sessions			
Is it feasible to train local lay	Fidelity to IPT	Percentage of session components rated	>60	30-59	<30
people and school nurses to		superior or satisfactory, averaged across			
deliver IPT?		observed sessions			
	Serious adverse events	Percentage difference in serious adverse	<4	4	5
		events in the intervention arm compared			
		to the control arm			
Are trial procedures	Eligible adolescents	Percentage of eligible adolescents with	>80%	50-80	<50
(randomisation and data	agree to participate	informed consent at baseline			
collection) acceptable to	Eligible schools agree to	Percentage of schools approached that	>60%	30-60	<30
participants and schools?	participate	agree to participate			
	Missing data	Percentage of missing items on primary	<15	15-50	>50
		and secondary outcome			
	Participant retention	Percentage of participants completing	>70%	30-70	<30
		the endline survey			
	t .		1	-1	

Table 3: Potential outcomes and tools

Outcome type	Outcome	Assessment timepoint	Potential tools	Notes
In-session	Depression	Start of each pre-group and group session	IPT-A in-session weekly symptom check	7 items, response options presented as emojis
	Satisfaction	Endline	Treatment satisfaction	Adapted from Mufson 2015.
Primary	Depression	Baseline, midline1, midline 2, endline and follow up	PHQ-A MMAP trans	
Secondary	Functional impairment	Baseline, midline1, midline 2, endline and follow up	Locally developed tool	Adapt for Chitwan and for boys and girls
	Anxiety	Baseline, endline and follow-up	Generalised Anxiety Disorder Assessment (GAD-7)	MMAP translation
	Post-traumatic stress disorder	Baseline, endline and follow-up	PCL-C (8-item abbreviated version of the PTSD Checklist 5)	
	School attendance	Baseline and endline	Number of days attended in the 18 school days prior to the baseline (excluding school closures and Saturdays)	Collect data from school register
	Educational performance	Endline	End of year examination	
	Quality of Life	Baseline and endline	EuroQol-5 Dimension 5 levels (EQ-5D)	
Intermediate	Норе	Baseline, midline 1, midline 2, endline, follow-up	Children's Hope Scale	6 items
	Emotion regulation	Baseline, midline 1, midline 2, endline, follow-up	Difficulties in Emotion Regulation Scale (DERS-SF) 18 items	Used in ALIVE

	Self efficacy	Baseline, midline 1, midline 2, endline, follow-up	General Self-efficacy Scale	
	Social support	Baseline, midline 1, midline 2, endline, follow-up	Multidimensional Scale of Perceived Social Support	Need to add to battery
	Group cohesiveness	(intervention group only) Midline 1, midline 2, endline, follow-up	PM+ Group Cohesiveness scale	Used in PM+
	IPT skills	Midline 1, midline 2, endline, follow-up	Interpersonal Psychology Skills Scale	
	Conflict reduction		Social Adjustment Scale Self Report	
Predictors	Socio-economic status	Baseline	Social and Economic Measure for Adolescents	
	School climate	Baseline, endline	Beyond Blues	Used in HASHTAG
	Gender norms	Baseline	Johns Hopkins Global Early Adolescent Study	9 items
	Adversity	Baseline	Johns Hopkins Global Early Adolescent Study	13 items
Caregiver	Socioeconomic status	Baseline	Social and Economic Measure for Caregivers	Used in ALIVE
	Depression	Baseline, endline	Patient Health Questionnaire 9 items	Used in ALIVE
	Parenting	Baseline, endline	Alabama Parenting Questionnaire 19 items	Used in ALIVE
	Disruptive behaviour	Baseline, endline	Disruptive Behavior International Scale – Nepal version (DBIS-N) 10 items	

Table 4: CMOCs and data to refine them

CMOC	Qualitative analysis	Quantitative analysis
CMOC 1 Context: For students of higher socioeconomic status not experiencing structural vulnerability or intractable adversity and having more opportunities to implement new strategies. Mechanism: IPT enables participants to participate in discussions through which they learn and implement strategies to develop hope, reduce conflict, build relationships and improve self-efficacy. Outcome: This generates reductions in depression	Analysis of SSI transcripts with participants from different socioeconomic backgrounds with and without exposure to adversity (direct and indirect probing on CMO). SSIs with facilitators, direct and indirect probing of marginalisation, exclusion by SES	Comparison of engagement - attendance, items 1-4 on group cohesion scale- by SES and exposure to adversity: Comparison of mean depression score (PHQ-A) by SES and exposure to adversity Comparison of ability to implement IPT-self efficacy, hope, conflict and relationship initiation/improvement- by SES and exposure to adversity
CMOC 2 Context: For students in schools with school climates characterised by strong student-staff and student-student relationships and norms of mutual respect and social support and thereby having more opportunities to implement new strategies. Mechanism: supportive for implementation or amenable for adolescents to implement ipt skills Outcome: This generates reductions in depression.	Analysis of SSI and FGD transcripts and transect walks with participants sampled to represent different school climates (baseline Beyond Blue score), facilitators, school principals, teachers and nurses probing on CMO	Comparison of mean depression score (PHQ-A) by Beyond Blue Score Comparison of ability to implement IPT-self efficacy, hope, conflict and relationship initiation/improvement-by Beyond Blue Score
CMOC 3 Context: For boys who do not experience cultural norms or structural violence which impede opportunities to implement new strategies. Mechanism: IPT enables participants to participate in discussions through which they learn strategies to develop hope, reduce conflict, build relationships and improve self-efficacy. Outcome: This generates reductions in depression.	Analysis of SSI and FGD transcripts with participants sampled to represent different genders and facilitators, caregivers and teachers probing on CMO	Comparison of ability to implement IPT-self efficacy, hope, conflict and relationship initiation/improvement by gender Comparison of scores on gender norm scale with ability to implement IPT, self efficacy, hope, conflict and relationship initiation/improvement

CMOC 4 Context: For older (and more cognitively able?) students more cognitively able to consider others' perspectives, learn negotiation skills, develop solutions to interpersonal problems, understand links between events and mood, manage anger and name and express emotions. Mechanism: IPT enables participants to participate in discussions through which they learn strategies to develop hope, reduce conflict, build relationships and improve self-efficacy. Outcome: This generates reductions in depression.	Analysis of SSI and FGD transcripts with older and younger participants and facilitators, caregivers and teachers probing on CMO	(SAS-SR), and depression (PHW-A) score Comparison of IPT knowledge test and IPT skills scores, emotion regulation (DERS) by age Comparison of depression outcomes (PHQ-A) by age
CMOC 5 Context: For students participating in initial sessions and participating in discussions which validate participants' experiences and instil hope. Mechanism: IPT enables participants to develop hope and motivation to engage in the intervention. Outcome: This generates immediate reductions in depression.	Analysis of SSI and FGD transcripts with participants and facilitators probing on CMO	Exploring temporal relationship between hope and PHQ-A score by plotting baseline, midline and endline data.

Table 5: Process evaluation data collection in the intervention arm

Method	Timing	Process indicator
Quantitative attendance data collected by IPT facilitators at each group session	Throughout intervention	Dose
Intervention fidelity data collected using the IPT checklist by clinical supervisors	For each group: 1 observation in the initial phase, 2 observations in the middle phase and 1 observation of the termination phase (4 per group)	Fidelity
Unstructured observation by clinical supervisors – field notes about IPT sessions and informal conversations	For each group: 1 observation in the initial phase, 2 observations in the middle phase and 1 observation of the termination phase (4 per group)	Fidelity, context, mechanism
Transcripts of IPT group sessions	For each group: 1 observation in the initial phase, 2 observations in the middle phase and 1 observation of the termination phase (4 per group)	Mechanism
Notes on supervisory meetings between clinical supervisors and facilitators	Throughout intervention	Fidelity, mechanism
Facilitator competency data collected using ENACT and GroupACT	Pre-training, post training (ENACT and GroupACT), in-vivo (initial, middle and termination group sessions (GroupACT only in parallel with IPT checklist)	Fidelity, mechanism
Interviews with participants (n=20)	Spread interviews over endline and follow-up	Context, mechanism
Group discussion with facilitators (n=2)	Endline	Fidelity, context, mechanism
Interview with school teachers/principals	Endline	Context, mechanism
Interview with school staff – school nurses, school principals, teachers (n=17-20)	Endline	Context, mechanism
Interview with caregivers (n=10)	Endline	Context, mechanism
Midline quantitative surveys with IPT participants to measure intermediate outcomes	After group session 2 and 6	Mechanism

Figures

[figure not shown]

Figure 1: Overall programme of work

[figure not shown]

Figure 2: Interpersonal therapy theory of change

[figure not shown]

Figure 3: Participant flow chart

Commented [RCK1]: I removed the Figure with the maps because of the potential copyright and problems if we publish. I think I copied the maps from Wikipedia!

Month			1	Nov			De	С				Jan				F	eb			Λ	⁄lar				Apr				May		
Week commencing	30	6	13	20	27	4	11	18	25	1	8	15	22	29	5	12	19	26	4	11	18	25	1	8	15	22	29	6	13	20	27
				PG1	PG2	G1	G2	G3	G4	G5	G6	G 7	G8	G9	G10																
Strata 1	Screen	Baseline	festival				M1				M2					End	dline					Exams							llow- up		
			Tihar f			PG1	PG2	G1	G2	G3	G4	G5	G6	G7	G8	G9	G10					Exa									
Strata 2				Screen	Baseline				M1				M2					Endl	line											Follo u	

Figure 4: Timeline of assessments

Figure 5: Masking in the trial team

TRAINING CONTENT	RECRUITMENT CRITERIA Essential Education 10+2. Aged 20-25 years Nepali citizenship Able to reside in Chitwan during the trial Desirable Experience working with adolescents Experience working in an NGO	MODULE 1: FOUNDATIONAL HELPING SKILLS (10 days) Nonverbal communication and active listening Verbal communication skills Confidentiality Rapport building and self-disclosure Exploration, interpretation and normalisation of feelings Empathy, warmth and genuineness Assessment of harm Connecting to social functioning and impact on life Causal and explanatory models Involvement of family Goal setting Promotion of hope Coping mechanisms Psychoeducation Eliciting feedback	MODULE 2: GROUP MANAGEMENT SKILLS (1 day?) Collaboratively develop and regularly review group ground rules and guidelines Participation of all group members Fostering empathy between group members Guiding collaborative proble—solving Mitigating barriers to attendance Confidentiality among group members Time management and pacing	MODULE 3: INTERPERSONAL THERAPY Didactic workshop (5 days) • Principles and theory • Initial, middle and termination phases • Safety planning • Treatment techniques Supervision of practice cases • Minimum of 2 individual cases and one group
ASSESSMENT TOOL	INTERVIEW	ENACT	GROUP-ACT	IPT KNOWLEDGE TEST IPT CHECKLIST

Figure 6: Training programme for IPT facilitators

^{*}Black indicates the team member is masked to allocation

	Enrolment		Follow-up				
TIMEPOINT**	Aug-Sep 23	Sep – Oct 23	Nov – Dec 23	Jan – Feb 24	Feb - Mar 24	Apr – May 24	Jun – Jul 24
ENROLMENT:							
School recruitment							
Participant screening							
Allocation							
INTERVENTIONS:							
Interpersonal therapy							
Enhanced usual care							
ASSESSMENTS:							

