Randomisation will be at the school level and stratified according to whether recruitment at the school includes adolescents from class 11 or not. In total there will be three strata: Strata 1 will comprise two of the four schools from which we are recruiting adolescents in class 8, 9 and 11. Strata 2 will comprise the two remaining schools in class 8, 9 and 11. Strata 3 will comprise schools where we are recruiting in class 8 and 9 only. We will complete screening and the baseline survey in Strata 1 (which will take approximately two weeks) then randomise these schools with a 1:1 allocation ratio to the intervention and control arms. The intervention will then start in these schools. After Strata 1 schools have been allocated, screening and baseline will start in Strata 2 after which these schools will be randomly allocated to the intervention and control arms. The process will then be repeated in Strata 3. In Strata 1 and 2 there are two schools with four groups per school (eight adolescents per group): one male and one female group for Class 8 and 9 combined, one male and one female group for Class 11. In Strata 3 there are four schools with two groups per school: one male and one female for Class 8 and 9 combined. Advantages for stratifying in this way include: (i) the duration between identifying that an adolescent is depressed and the adolescent starting the intervention is minimised; (ii) a staggered start to the surveys meaning fewer research assistants are needed over the course of the trial; (iii) randomisation can be conducted after baseline with minimal delay. The randomisation will be done by a masked, independent researcher.

Masking and concealment

Research and clinical staff will work independently from separate offices in Chitwan. Figure 5 indicates which members of the trial team will be masked to allocation. Research assistants conducting baseline, midline, endline and follow-up surveys will not be given information about the allocation of schools. Due to the participatory nature of the intervention, adolescents, school staff, IPT facilitators and research assistants conducting the process evaluation will not be masked to allocation. The statistician conducting the final analysis of the pilot trial data will be masked. We will attempt masking at the cluster level: individual schools will not know if they have been allocated to the intervention or control.

Sample size

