Research assistants will mainly conduct screening, baseline, endline and follow-up interviews at school in a private place. If participants are not attending school regularly, research assistants will ask to conduct an interview in the participant's home. The interviews will last around one hour. In interviews, the research assistants will administer surveys to the participants primarily face-to-face in their school, outside class hours. We will collect data on demographic characteristics (age, gender, religion, caste/ethnicity, level of education), socioeconomic background (income sufficiency, main source of income), target primary (depression), secondary (anxiety, PTSD, functional impairment, school attendance and achievement) and intermediate outcomes (hope, self-esteem, emotion regulation, interpersonal conflict, interpersonal skill use, and social support for both arms, and group cohesion for intervention arm only) and predictors (school climate, gender norms, and adversity). We will use the KoboToolbox data collection platform. Research assistants will

enter data on mobile phones or tablets. We will use automated skip patterns and consistency logic to reduce errors and missing data. We will collect data on school attendance at baseline and endline from school registers.

We will use school and telephone contact to try to follow up all participants. In the feasibility study, COVID-19 lockdown restrictions forced us to conduct some of the baseline survey interviews and all the follow-up interviews by phone. Using regression analysis with tests for interaction, we tested whether the change in mental health outcomes between post-treatment and follow-up differed by whether the post-treatment interview was conducted on the phone or in person. We found no statistically significant differences in depression scores between individuals who had their post-treatment interview conducted in person v. over the phone although the sample size was small (n=25, mean difference 0.9, 95% CI -1.7 – 3.5), . In the pilot trial, we will consider phone-based interviews for participants who move out of the area whom we cannot meet in person and further explore any differences that arise by mode of interview.

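### An intervention-only group cohesion scale sits in the surveys run by masked assessors and can disclose a school's arm; the statement on school-level masking also contradicts itself

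*Protocol*

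**What the plan says.** **Assessor masking (Protocol, Masking and concealment).** "Research assistants conducting baseline, midline, endline and follow-up surveys will not be given information about the allocation of schools". Those listed as unmasked are "adolescents, school staff, IPT facilitators and research assistants conducting the process evaluation will not be masked to allocation". Among research assistants, only the process-evaluation ones are on that list.

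**How the survey is run (Data collection, management and monitoring).** "In interviews, the research assistants will administer surveys to the participants primarily face-to-face in their school, outside class hours". Answers are entered by the assistant on a phone or tablet, with automated skips. The intermediate outcomes listed there end with "and social support for both arms, and group cohesion for intervention arm only".

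**When the scale is given (Table 3).** The row for group cohesiveness reads "intervention group only) Midline 1, midline 2, endline, follow-up". The PHQ-A row covers baseline and those same four rounds.

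**School-level masking (Masking and concealment).** The protocol says it will attempt masking at cluster level, so that "individual schools will not know if they have been allocated to the intervention or control". The Intervention section has the groups meeting in a room at the school.

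**The concern.** An interviewer who reads out items about a therapy group learns that the participant was in one. If the form omits the items, it must be driven by the arm, or by a question whose answer gives the arm away. Since schools are randomised, what is learned from one participant applies to everyone at that school.

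The PHQ-A is the target primary outcome for phase III. It is administered by an interviewer to adolescents who know their allocation, so assessor masking is the main protection left against detection bias. The pilot also asks, among its research questions, whether masking is feasible. An instrument that discloses the arm by design blurs the answer, and the data sources in Table 1 for that question include no measure of whether survey assistants became aware of allocation.

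The sentence on school masking is a second problem in the same section. Staff of a school that hosts weekly groups cannot be both unmasked and unaware of the school's allocation.

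**Working it through.** The plan gives no figure on this point. The check sets the sections side by side and then counts the exposed interviews.

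**1. Who asks the scale?**
- Masking and concealment: the assistants running all survey rounds, midlines included, are on the masked side.
- Data collection: research assistants administer the surveys, and cohesion is part of the listed survey content for one arm.
- Table 3: cohesion is scheduled at 4 of the 4 post-baseline rounds, each of which includes the PHQ-A.
- Process evaluation: the unmasked assistant's stated task is qualitative interviews and focus groups. The cohesion scale is not mentioned.

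No single sentence says that the masked assistant asks the cohesion items. That follows from reading these sections together. No dummy module, self-completion or separate interviewer is described.

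**2. How far does one disclosure reach?** There are 8 schools, 4 per arm. Strata 1 and 2 have two schools each, allocated 1:1, so knowing one school's arm gives the other's. An assistant who knows that the module exists also learns from its absence.

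**3. How many interviews?** From the Randomisation and Sample size sections:
- Strata 1 and 2: 2 schools × 4 groups × 8 = 64 each. Stratum 3: 4 schools × 2 groups × 8 = 64. Total 192, which matches the stated sample size.
- Intervention arm: 32 + 32 + 32 = 96.
- All four post-baseline rounds, before attrition: 96 × 4 = 384 interviews with the module, out of 192 × 4 = 768 PHQ-A interviews.
- Endline and follow-up only: 96 × 2 = 192 out of 192 × 2 = 384.

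**4. How many PHQ-A interviews come before an assistant's first exposure at a school?** The protocol gives neither the module order nor the number of assistants. Assume that the PHQ-A comes first, that 1 to 4 assistants work per school, and that an assistant is exposed by the first interview there.
- Same assistants in every round: 8 × 1 = 8 to 8 × 4 = 32 of 768, or 1.0% to 4.2%.
- New assistants in each round who share nothing: 8 × 4 = 32 to 32 × 4 = 128 of 768, or 4.2% to 16.7%.
- Endline and follow-up only, same assistants: 8 to 32 of 384, or 2.1% to 8.3%.

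If the module or its form branch precedes the PHQ-A, fewer interviews are protected. Under each of these assumptions, most post-baseline PHQ-A interviews follow a possible disclosure.

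**The case against.** **The midline administrator is uncertain.** Table 5 lists the midline surveys of IPT participants under process evaluation without naming who runs them, and the data collection section omits midline when it says which interviews the assistants mainly conduct. An unmasked assistant may have been intended. Figure 5, on masking in the team, is not shown in the text available. This stands as a doubt. Against it, the masking section names midline among the masked surveys, and the Design section has both arms assessed at midline. The doubt does not touch endline or follow-up.

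**The promise is narrow.** The protocol undertakes only that assistants are not told the allocation. That is literally kept, but the form can supply what nobody tells them.

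**Other leaks exist.** Unmasked adolescents and staff may disclose the arm anyway. True, so the fix reduces unmasking and does not secure masking. Such disclosure is incidental, whereas this route is built into the schedule.

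**The pilot itself is little affected.** Its primary outcome is progression, no criterion in Table 2 compares PHQ-A between arms, and arm differences are estimated without testing. This stands: the preliminary effect estimates could be distorted, but the progression criteria do not depend on them.

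**Stronger readings that a reader might infer.** One is that all eight schools are revealed by midline 1. That needs assumptions about who runs midline and which assistants return to which school, and the protocol states neither. Another is that the pilot would judge masking to have failed. Masking is a research question, but Table 2 has no masking indicator. A third is that treatment satisfaction is a further leak. Table 3 schedules it at endline beside the in-session measure, and its administrator is not stated.

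**Conclusion.** The concern holds in limited form. The protocol keeps its survey assessors masked and also places an intervention-only scale in the surveys they administer, with no safeguard described. Disclosure is a clear risk at endline and follow-up, and a likely one at the two midlines. On planned numbers the scale is attached to up to 384 of 768 post-baseline PHQ-A interviews, or 192 of 384 if only endline and follow-up count.

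This rests on the cohesion items being asked within the same interview as the PHQ-A, which the sections imply but no sentence states. It shows a route to unmasking, not that unmasking or biased scoring occurred. The consequence falls mainly on phase III and on how the pilot reports masking.

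The contradiction about schools is separate. Even with the wording that masking will be attempted, it cannot be reconciled with unmasked staff and sessions on the premises.

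**What to change.** - Use one identical interviewer-administered survey in both arms. Collect group cohesion after the PHQ-A on a sealed self-completed form, or through the unmasked process-evaluation assistant where capacity allows. Treat treatment satisfaction the same way if it is in the same interview.
- The sealed form must not itself mark the arm. Have someone other than the assessor hand it out, or give same-looking envelopes in both arms.
- Apply this to phase III, and to any remaining pilot surveys by assistants not yet unmasked. As of July 2024 the groups had finished and endline and follow-up surveys were under way. Changing the form now cannot re-mask an assistant who already knows a school's arm.
- Report the pilot's survey assessors as potentially unmasked after baseline.
- Correct the sentence on school-level masking so that it agrees with the unmasked status of school staff.

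**Cost.** A short extra form for about 96 intervention participants per round. The self-completed version needs no new staff. Using the process-evaluation assistant would mean up to 96 × 4 = 384 extra contacts for what the protocol describes as one dedicated person, and it already restricts caregiver interviews to Stratum 3 for lack of assistants. Disclosure by participants or staff would remain possible.
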